1. INTRODUCTION

[figure not shown]
This document describes the statistical methods and data presentations planned for the analysis of the efficacy and safety data from Protocol CVL-751-PD-003. Background information is provided for the study designs and objectives. Further details of study conduct, and data collection are provided in the study protocol and electronic case report forms (eCRFs).

1.1. Study Overview

This is a prospective, Phase 3, multicenter, multinational, randomized, double blind, placebo controlled, parallel group, 27 week trial to evaluate the efficacy, safety, tolerability, and pharmacokinetics (PK) of flexible doses of tavapadon (5 mg to 15 mg once daily [QD]) as adjunctive therapy to levodopa (L Dopa) in male and female subjects aged 40 to 80 years who have a diagnosis of PD (consistent with the UK Parkinson's Disease Society Brain Bank diagnostic criteria); a modified Hoehn and Yahr score of 2, 2.5, or 3 in the "on" state; a minimum of 2½ hours of "off" time on 2 consecutive days; and a good response to L Dopa in the judgment of the investigator. The trial will include a Screening Period (maximum of 4 weeks), a 27 week Treatment Period, and a 4 week Safety Follow up Period. Details of schedule of assessments are provided in [Section 9.2](#).

A total of 368 subjects are planned to be randomized in a 1:1 ratio to receive tavapadon or placebo once daily (184 subjects per treatment group). The dose of tavapadon will be titrated and adjusted over the first 13 weeks of the trial and then maintained for 14 weeks. The planned duration of treatment is 27 weeks, including the Titration and Maintenance Phases. The investigational medicinal products (IMPs) will be taken orally.

The trial design is depicted in [Figure 1](#).

Figure 1: Trial Schematic

1.2. Sample Size Considerations

A sample size of 184 subjects per group (total, 368 subjects) will provide at least 90% power to detect a change in the primary outcome measure (change from baseline in "on" time without troublesome dyskinesia) of 1 hour with a standard deviation of 2.5, a 2 sided alpha level = 0.049, and assuming a 27% dropout rate. The sample size calculation was based on a two-sample t-test with equal variance.

Given that the assumptions for the sample size were based on a preliminary study of limited sample size using a different dosing schedule, it is unknown if the assumption of a standard deviation of 2.5 is a reasonable estimate of the population variability and appropriate for this study as designed. To this end, an interim analysis of the primary efficacy endpoint will be included to assess the adequacy of the overall sample size relative to achieving the study objectives. [Section 9.1](#) provides further detail on the conduct of the interim analysis. Should the interim analysis indicate a requirement of sample size increase per pre-defined decision rule ([Section 9.1](#)) to maintain statistical power, Cerevel will extend enrollment to achieve the required sample size.

In the event of higher than anticipated early terminations due to COVID-19 or other reasons, Cerevel may also extend enrollment in order to maintain the planned statistical power.

1.3. Measures to Minimize Bias: Randomization and Blinding

1.3.1. Subject Assignment to Treatment

All subjects will be centrally randomized in a 1:1 ratio to 2 treatment arms (tavapadon 5 to 15 mg QD or placebo) at the Baseline Visit via an Interactive Voice Response System/Interactive Web Response System (IVRS/IWRS), according to a computer generated randomization scheme generated by a non-study statistician and be kept strictly confidential. Subjects will be sequentially assigned to the next available randomization number and will receive the IMP that corresponds to that randomization number. Once a randomization number has been assigned, it will not be reassigned.

1.3.2. Blinding

The tavapadon and placebo tablets will be identical in appearance and will be packaged in identically appearing blister cards. All subjects will take 3 tablets once daily of IMP during the Treatment Period, either all tavapadon tablets, all placebo tablets, or a combination of tavapadon and placebo tablets. Tablets will be packaged to allow dosage adjustments (as shown in [Table 1](#)) to be made without breaking the trial blind.

Treatment assignments will be blinded to the investigators and other trial site personnel, the subjects, and all sponsor personnel who are involved in the conduct of the trial (including trial monitoring, data management, and data analysis). Access to the treatment codes will be restricted to personnel who are responsible for generating and maintaining the randomization code, packaging the IMPs, operating the IVRS/IWRS, analyzing the PK blood samples, or reporting serious adverse events (SAEs) or adverse events of special interest (AESI) to regulatory agencies.

Documentation of breaking the blind should be recorded in the subject's medical record and eCRFs, with the reason for breaking the blind, the date and time the blind was broken, and the names of the personnel involved. Once the blind is broken for a subject, treatment with the IMP may not be reinitiated for that subject.

1.4. Treatment Period

The dose of tavapadon will be gradually titrated to 15 mg QD in all subjects over the first 14 weeks of the trial during the Dose Titration and Dose Adjustment Phases unless prevented by intolerance. A reduction in dose (from 15 mg QD to 10 mg QD or from 10 mg QD to 5 mg QD) will be allowed based on individual subject tolerability. Subjects who require a dose reduction may be rechallenged with the higher dose, at the discretion of the investigator, to address symptomatic needs.

The titration schedule, as shown in [Table 1](#), will be used for all subjects who are randomized. Subjects will take 3 tablets of IMP, either all tavapadon tablets, all placebo tablets, or a combination of tavapadon and placebo tablets, throughout the trial to maintain the trial blind.

Table 1: Tavapadon and Placebo Dosing Schedule

Trial Day	Titration Step	Blinded Treatment Assignment
		Maintenance Phase^c
		Maximum tolerated tavapadon dose (5-15 mg) or placebo QD

Abbreviation: QD = once daily.

- a. No deviations in the titration schedule up through 5 mg QD (████████) will be allowed.
- b. The dose will be adjusted over the range of 5 to 15 mg ████████ based on individual subject tolerability.
- c. Subjects will receive the highest tolerated dose level that is achieved during the Dose Adjustment Phase. No adjustment will be allowed during the Maintenance Phase.

No deviations in the titration schedule up through █████ (5 mg QD) will be allowed. Titration of tavapadon should be guided by absence of tolerability issues that are reported as AEs and that are of sufficient severity resulting in significant dysfunction or distress to the subject. Any questions regarding tolerability issues and titration should be directed to the medical monitor before adjustments are initiated. The dose of tavapadon will be gradually titrated to the █████ dose (15 mg QD) in all subjects, as shown Table 1, unless prevented by intolerance.

Subjects who are unable to achieve or tolerate the █████ dose (15 mg QD) may receive the █████ dose (10 mg QD). Subjects who cannot achieve or tolerate the █████ dose (10 mg QD) may receive the █████ dose (5 mg QD). Subjects who cannot achieve or tolerate the █████ dose (5 mg QD) will be discontinued from the trial. Subjects who require a dose reduction may be rechallenged with a higher dose to address symptomatic needs after at least 7 days at the lower dose during the Dose Adjustment Phase.

Subjects will receive the highest tolerated dose level that is achieved during the Dose Adjustment Phase for the duration of the subsequent 13-week Maintenance Phase. Adjustments in the dose of tavapadon will not be allowed during the Maintenance Phase. Subjects who cannot tolerate their maintenance dose will be discontinued from the trial. Subjects will be considered to have completed this trial once they complete the assessments that are scheduled at the Week 27 visit.

2. OBJECTIVES AND ENDPOINTS

The trial objectives and endpoints are summarized in [Table 2](#).

Table 2: Objectives and Endpoints

Objectives	Endpoints
Efficacy	
Primary
 
 To assess the effect of tavapadon on the change from baseline in total daily hours of “on” time without troublesome dyskinesia in L-Dopa-treated subjects with PD who are experiencing motor fluctuations 
Secondary
 
 To assess the effect of tavapadon on the change from baseline in total daily hours of “off” time in L-Dopa treated subjects with PD who are experiencing motor fluctuations
Safety and Tolerability	
Primary Efficacy Endpoint
 
 Change from baseline to endpoint in total “on” time without troublesome dyskinesia based on the 2-day average of the self-completed home diary for motor function status (Hauser diary) 
Key Secondary Efficacy Endpoint
 
 Change from baseline to endpoint in total daily “off” time based on the 2-day average of the self-completed home diary for motor function status (Hauser diary) 
Secondary Efficacy Endpoints (at all time points)
 
 Change from baseline in the total “on” time without troublesome dyskinesia based on the 2-day average of the self-completed home diary for motor function status (Hauser diary) Change from baseline in the total “off” time based on the 2-day average of the self-completed home diary for motor function status (Hauser diary) Change from baseline in the MDS-UPDRS Part I score Change from baseline in the MDS-UPDRS Part II score Change from baseline in the MDS-UPDRS Part III score 
Other Endpoints
 
 Change from baseline in the PDQ-39 score Change from baseline in the EQ-5D-5L index and VAS scores 
QUIP-RS
 
ESS
 
C-SSRS
 
Nature, frequency, and temporality of TEAEs, including abuse-related AEs and AEs related to MHIs
 
Clinical laboratory evaluations
 
Vital signs
 
Physical examinations
 
ECGs

Objectives	Endpoints
Pharmacokinetic	

 To evaluate the PK of tavapadon in this population 	Plasma concentrations of tavapadon and its metabolite (if required) at baseline (Day 1) and at Weeks 5, 11, 14, 22, and 27

Abbreviations: AE = adverse event, C-SSRS = Columbia-Suicide Severity Rating Scale, ECG = electrocardiogram, EQ-5D-5L = EuroQol 5 Dimension 5 Level, ESS = Epworth Sleepiness Scale, L-Dopa = levodopa, MDS-UPDRS = Movement Disorder Society-Unified Parkinson's Disease Rating Scale, MHIs = medication handling irregularities, PD = Parkinson's disease, PDQ-39 = 39-Item Parkinson's Disease Rating Scale, PK = pharmacokinetic, QUIP-RS = Questionnaire for Impulsive-Compulsive Disorders in Parkinson's Disease-Rating Scale, TEAEs = treatment-emergent adverse events, VAS = visual analog scale.

3. KEY ASSESSMENTS AND DERIVATIONS

3.1. Efficacy Assessments

3.1.1. Hauser Diary

The Hauser diary assesses patient-defined motor function status over a period and provides a tool for assessment of change in “off” time and “on” time with troublesome dyskinesia ([Hauser et al, 2000](#)). The Hauser diary asks patients to rate their mobility for each 30 minute period and to record their status for the majority of the period in 1 of 5 categories as: “on” time without dyskinesia, “on” time with non-troublesome dyskinesia, “on” time with troublesome dyskinesia, “off” time, or asleep.

Subjects will record diary entries at home at 30 minute intervals for 24 hours on 2 consecutive days within the 7 days before randomization at the Baseline Visit and at 30 minute intervals for 24 hours on 2 consecutive days within the 7 days before each postbaseline clinic visit.

Valid Hauser diaries should contain no more than 2 hours (four 30-minute periods) of missing entries total per 24 hours diary. If a diary contains more than 2 hours of missing data, it will not be considered valid. Valid diaries of the 2 days prior to a given visit should be averaged for the parameters needed for analysis.

3.1.1.1. Derivation of ‘ON’ Time Without Troublesome Dyskinesia for Each Visit

The key endpoint ‘ON’ time without troublesome dyskinesia for a given day is defined as the sum of “on” time without dyskinesia and “on” time with non-troublesome dyskinesia of the day. The analysis value for a given visit is defined as the average number of ON’ hours without troublesome dyskinesia as recorded in the subject diary prior to a given office visit. To be included in the average, the subject diary must be deemed valid as defined above. The analysis value of ‘ON’ time without troublesome dyskinesia for each visit is calculated using the following formula:

$$t_{on} = \frac{1}{2} \sum_{i=1}^2 t_i$$

where t_i is the 'on' time without troublesome dyskinesia in the i -th day ($i = 1, 2$) prior to each visit.

3.1.1.2. Derivation of 'OFF' Time for Each Visit

'OFF' time is defined as the average number of 'OFF' hours as recorded in the valid subject diary prior to a given office visit. To be included in the average, the subject diary must be deemed valid as defined above. 'OFF' time for each visit is calculated using the following formula:

$$t_{off} = \frac{1}{2} \sum_{i=1}^2 t_i$$

where t_i is the 'off' time in the i -th day ($i = 1, 2$) prior to each visit.

3.1.1.3. Handling Missing Hauser Diary Entries

If less than 2 valid diaries are returned by the subject for a given visit, the following method for calculating the average parameters will be followed:

- If only 1 of the daily diaries is valid then it will be used to calculate the average parameters
- If there are no valid subject diaries for a particular visit, then the data will be considered missing for that visit

In the case of a missing entry in a specific 30-minute time slot for a valid Hauser diary day (i.e. less than 2 hours missing per day), the missing slot will be imputed by carrying forward the value of the last 30-minute epoch prior to time slot of the missing value (a last observation carried forward (LOCF) approach) unless the previous 30-minute slot is on the prior day. In the case when the LOCF is not feasible (either the prior slot is also missing or the prior slot is not on the same day), the entry of the time next slot will then be carried backward (NOCB) to impute the missing slot. In the unlikely event of 2 or 3 consecutive missing time slots on a day with valid day of Hauser diary, the approach will be applied consecutively to fill the missing slots.

3.1.2. Movement Disorder Society-Unified Parkinson's Disease Rating Scale (MDS-UPDRS)

The MDS UPDRS ([Goetz et al, 2008](#)) is a multidimensional scale that assesses the motor and nonmotor impacts of PD across 4 parts. The scale is completed using a combination of physician and patient assessments and a collection of information from the patient or caregiver:

- Part I, nonmotor aspects of experiences of daily living, comprises 13 items, 6 of which are rated by the physician (Part IA) and 7 of which are rated by the patient (Part IB).
- Part II, motor aspects of experiences of daily living, comprises 13 items that are rated by the patient. The 13 items in Part II and the 7 items in Part IB constitute the patient questionnaire portion of the MDS UPDRS.

- Part III, motor examination, comprises 18 items that are assessed by the investigator (resulting in 33 scores by location and lateralization).
- Part IV, motor complications, comprises 6 item (3 items for dyskinesia and 3 items for fluctuation) and requires the physician to use historical and objective information to assess dyskinesia and motor fluctuations.

Each item is rated on a scale from 0 to 4 on which 0 = normal, 1 = slight, 2 = mild, 3 = moderate, and 4 = severe.

Whenever possible, the same individual should perform the ratings for an individual subject throughout the course of the trial. The postbaseline MDS UPDRS assessments Parts I, II, and III should be conducted approximately 2 to 3 hours after the last dose of L-Dopa on the day of the clinic visit. Part IV is not to be assessed in this study as more detailed data will be collected through Hauser diary.

3.1.2.1. Handling of Missing Items from MDS-UPDRS

If individual items are missing from a given part of the MDS-UPDRS, the corresponding total score may be generated by prorating the response if the number of missing items is not excessive. A single missing value in Parts I, II, and IV is allowable. For Part III, up to 7 values may be missing. To prorate the value, the following formula is utilized:

$$P = \left(\frac{\sum_{i=1}^n j_i}{n} \right) U$$

Where n is the number of non-missing items, j_1-j_n represents the n non-missing values reported by the subject for the given subscale, and U is the number of total items in the given Part of the scale.

3.1.3. 39-Item Parkinson's Disease Questionnaire

The 39-item Parkinson's Disease Questionnaire (PDQ-39) measures 39 items, which assess 8 domains of health: mobility (10 items), activities of daily living (6 items), emotional well being (6 items), stigma (4 items), social support (3 items), cognitions (4 items), communication (3 items), and bodily discomfort (3 items) (Peto et al, 1998). Each item is scored on the following scale: 0=never, 1=occasionally, 2=sometimes, 3=often, and 4=always. Items in each subscale and the total scale can be summarized into an index and transformed linearly to a scale from 0 (perfect health as assessed by the measure) to 100 (worst health as assessed by the measure).

A dimension score is calculated using the following formula:

$$d = \frac{1}{n * 4} \sum_{j=1}^n t_j * 100$$

where n is the number of items in the dimension, and t_j is the j^{th} item in the dimension. This transforms the scale linearly from 0 (perfect health as assessed by the measure) to 100 (worst health as assessed by the measure). If items are missing within a domain, the n in the above formula will be changed to the number of items in the dimension that the subject answered if at least half of the questions in the domain were answered. Otherwise, a domain and summary index will not be calculated.

A summary index called PDQ-39 SI, is calculated as the average of the 8-dimension scores.

3.1.4. EuroQol 5 Dimension 5 Level

The EuroQol 5 Dimension 5 Level (EQ 5D 5L) is a patient-reported outcome that measures health in 5 dimensions. It is a widely used survey instrument for measuring economic preferences for health states, is applicable to a wide variety of health conditions and treatments, and provides a simple descriptive profile and a single index value for health status (Herdman et al, 2011). The EQ 5D 5L consists of a descriptive system and a visual analog scale (VAS).

The descriptive system comprises 5 dimensions: mobility, self care, usual activities, pain/discomfort, and anxiety/depression. Each dimension has 5 levels: no problems, slight problems, moderate problems, severe problems, and extreme problems. The patient is asked to indicate his or her health state by ticking the box next to the most appropriate statement in each of the 5 dimensions (Section 9.3). This decision results in a 1 digit number that expresses the level that was selected for that dimension. The digits for the 5 dimensions are combined into a 5 digit number that describes the patient's health state. For example, 11122 would represent the health state for someone who has no problems with mobility, self-care, or usual activities, but who has slight pain or discomfort and slight anxiety or depression. For each subject and visit, the 5-digit health state will be converted into a single summary index, the EQ-5D Index, using the EQ-5D-5L Index calculator with US value set (van Hout, Janssen et al. 2012).

The EQ VAS records the patient's self-rated health on a 20-cm vertical visual analogue scale (VAS). The VAS is numbered from 0 to 100 with 0 meaning 'the worst health you can imagine' and 100 meaning 'the best health you can imagine'. This information can be used as a quantitative measure of health outcome that reflects the patient's own judgement. The EQ-5D-5L asks respondents to simply 'mark an X on the scale to indicate how your health is TODAY' and then to 'write the number you marked on the scale in the box below'.

3.2. Safety Assessments

3.2.1. Questionnaire for Impulsive-Compulsive Disorders in Parkinson's Disease Rating Scale (QUIP-RS) Scores

The QUIP RS has 4 primary questions that pertain to commonly reported thoughts, urges/desires, and behaviors associated with impulse control disorders (ICDs), each of which is applied to 4 ICDs (compulsive gambling, buying, eating, sexual behavior) and 3 related disorders (medication use, punding, and hobbyism).

Each question is scored using a 5 point Likert scale (score, 0=never [not at all], 1=rarely [infrequently or 1 day/week], 2=sometimes, 3=often, 4=very often). Scores for each ICD and

related disorder range from 0 to 16, with a higher score indicating greater severity (frequency) of symptoms.

The total QUIP-RS score for all ICDs and related disorders combined ranges from 0 to 112. In case of missing item scores, the missing value will be replaced by the average of non-missing scores at the same visit from the same subject. In case all item scores are missing, the total score will be set as missing.

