3.2.2. Epworth Sleepiness Scale (ESS) Total Score

The ESS scale is used to determine the level of daytime sleepiness. There are 8 situations listed for which patients rate their likelihood of dozing or sleeping (0=would never nod off, 1=slight chance of nodding off, 2=moderate chance of nodding off, or 3=high chance of nodding off). The total score is the sum of 8 item scores and can range between 0 and 24. The higher total score indicates the higher level of daytime sleepiness. A score of 10 or more is considered sleepy, and a score of 18 or more is very sleepy.

In case of missing item scores from the ESS, the missing value will be replaced by the average of non-missing scores at the same visit from the same subject. In case all item scores are missing, the total score will be set as missing.

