5.15.2. Epworth Sleepiness Scale (ESS)

The ESS individual questions and total score and corresponding changes from baseline will be summarized by treatment group and study visit. The percentage of subjects with sleepy (10 or more) and very sleepy (18 or more) scores will also be summarized. ESS individual question score as well as the total score will be presented in a listing. The ESS total score will also be analyzed using the same method (MMRM analysis) described in [Section 5.9.2](#) to explore any treatment difference in sleepiness.

5.15.3. Questionnaire for Impulsive-Compulsive Disorders in Parkinson Disease Rating Scale (QUIP-RS)

The QUIP-RS component scores (Gambling, Sex, Buying, Eating, Hobbyism-Punding, PD Medication Use), total ICD score, and total score and corresponding changes from baseline will be summarized by treatment group and study visit. QUIP-RS individual data will be presented in a listing. The total ICD score will also be analyzed using the same method (MMRM analysis) described in [Section 5.9.2](#) to explore any treatment difference in impulsive-compulsive behaviors.

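### The SAP fills missing ESS and QUIP-RS items with no minimum number of answers and, read literally, across QUIP-RS disorders, so scores can be inflated or diluted

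*SAP*

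**What the plan says.** SAP 3.2.1 describes the QUIP-RS as four questions, "each of which is applied to 4 ICDs (compulsive gambling, buying, eating, sexual behavior) and 3 related disorders (medication use, punding, and hobbyism". That is 28 items, each scored 0 to 4, and "The total QUIP-RS score for all ICDs and related disorders combined ranges from 0 to 112". The section then gives its only missing-data rule: "the missing value will be replaced by the average of non-missing scores at the same visit from the same subject". SAP 3.2.2 repeats the rule for the sleepiness scale: "In case of missing item scores from the ESS, the missing value will be replaced by the average of non-missing scores". For that scale, "The total score is the sum of 8 item scores and can range between 0 and 24". Both sections share one exception: "In case all item scores are missing, the total score will be set as missing".

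Neither section sets a minimum number of answered items. SAP 3.2.1 does not say whether the average is taken within a disorder or over the whole questionnaire. It gives no separate rule for the component scores or the ICD total.

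The same SAP is stricter for two efficacy scales:
- **MDS-UPDRS (SAP 3.1.2.1):** a part is prorated from its own items, with at most one missing value in Parts I, II and IV and at most seven in Part III.
- **PDQ-39 (SAP 3.1.3):** a domain is rescaled from its own items, and only "if at least half of the questions in the domain were answered". Otherwise neither the domain score nor the summary index is computed.

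SAP 5.15.2 summarises the ESS total, reports the percentages of subjects scoring 10 or more and 18 or more, and fits an MMRM to the total. SAP 5.15.3 summarises the QUIP-RS components, ICD total and overall total, and adds: "The total ICD score will also be analyzed using the same method (MMRM analysis".

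**The concern.** Filling a gap with a person's own item mean is reasonable when most items are answered and the items measure one thing. Neither condition is secured here. With one or two answers, almost the whole ESS total is extrapolated, and that total is then compared with fixed cut-offs. On the QUIP-RS, the literal rule lets answers about hobbyism, punding or medication use set a score for gambling or sexual behaviour, and so enter an ICD total meant to cover only the four ICDs.

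These scales bear on a stated aim of the programme. Protocol 2.1 says tavapadon is intended to limit adverse events linked to D2/D3 agonists, and it names impulse control disorders and sleep disorders among them. Subject-level scores on the two scales should therefore reflect what subjects answered.

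**Working it through.** **Inputs.** ESS: 8 items scored 0 to 3, cut-offs 10 and 18 (SAP 3.2.2). QUIP-RS: 4 questions × 7 disorders, items scored 0 to 4 (SAP 3.2.1). The stated ranges reproduce: 8 × 3 = 24 for the ESS; 4 × 4 = 16 per disorder and 7 × 16 = 112 for the QUIP-RS.

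**ESS.** With k items answered and observed sum S, the rule gives total = 8 × S/k. The smallest S that reaches a cut-off c is the first whole number at or above c × k/8. The most that can be imputed is 3 × (8 − k).

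| Items answered (k) | Smallest S for 10 or more (resulting total) | Smallest S for 18 or more (resulting total) | Most points imputed |
|---|---|---|---|
| 1 | 2 (16) | 3 (24) | 21 |
| 2 | 3 (12) | 5 (20) | 18 |
| 3 | 4 (10.67) | 7 (18.67) | 15 |
| 4 | 5 (10) | 9 (18) | 12 |
| 7 | 9 (10.29) | 16 (18.29) | 3 |

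A single answer of 3 yields the scale maximum, and a single answer of 0 yields 0.

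**QUIP-RS, inflation.** Take a subject with 3 on all eight hobbyism and punding items, the four sexual-behaviour items blank, and 0 on the rest.
- Answered items: 28 − 4 = 24. Sum: 8 × 3 = 24. Mean: 24/24 = 1.0.
- Imputed sexual-behaviour score: 4 × 1.0 = 4.
- ICD total: 0 + 0 + 0 + 4 = 4, with no ICD item endorsed.
- Under a within-disorder rule, the sexual-behaviour score and the ICD total would be missing.

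**QUIP-RS, dilution.** Take gambling 4, 4, 4, blank, with 0 on all other items.
- Answered items: 27. Sum: 12. Mean: 12/27 = 0.44.
- Gambling under the literal rule: 12 + 0.44 = 12.44.
- Gambling by within-disorder proration: (12/3) × 4 = 16.

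**No effect.** If every answered item is 0, the imputed value is 0 and nothing is added.

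**Effect of the PDQ-39 half rule.** The ESS total is unchanged with 4 to 7 items answered. With 1 to 3 answered it becomes missing. On the QUIP-RS, the inflation case becomes missing and the dilution case becomes 16.

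**The case against.** - **The QUIP-RS rule may not mean this.** The imputation sentence follows the definition of the overall total and ends by referring to the total, and it never says that the average crosses disorders. This stands in part: cross-disorder averaging is the literal reading but not an explicit one. If only the overall total was meant, the component scores and the ICD total have no missing-item rule, although SAP 5.15.3 summarises them and models the ICD total. Two programmers could implement this differently.
- **The examples are extremes.** This stands. They show what the rule permits, not what will happen. With one ESS item missing, at most 3 points are imputed.
- **The stakes are modest.** This stands. SAP 5.15.2 and 5.15.3 present both models as exploratory, and Protocol Table 10 plans only descriptive statistics for these scales. SAP 5.4 confines the controlled testing to the primary and key secondary endpoints. ESS item scores and individual QUIP-RS data are also listed, so an odd total could be traced.
- **The SAP has no single completeness convention.** This is true: its limits differ between MDS-UPDRS and PDQ-39, and nothing ties the half rule to these two scales. Both existing rules do, however, set a limit and stay within a part or domain.
- **Setting totals to missing has its own bias.** If sensitive sections are skipped because the behaviour is present, dropping those totals removes informative subjects. This stands, and the fix has to make the loss visible.

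**Conclusion.** The rule as written needs changing. It allows a full total from one answer and, read literally, scores one QUIP-RS disorder from answers about others. The scores affected are the ESS percentages at 10 or more and 18 or more; the QUIP-RS component, ICD and overall summaries; and the exploratory MMRMs of ESS total and ICD total. The primary and key secondary tests are unaffected.

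Four stronger readings are not supported:
- A reader might infer that the rule manufactures harm. The error runs both ways, as 4 where the score should be missing and 12.44 against 16 show.
- A reader might say that the first QUIP-RS subject's true ICD total is 0. The blank answers are unknown, so the right comparison is with missing.
- A reader might infer that the treatment comparison is biased by some amount. The documents give no item-missingness rate, overall or by group, so neither size nor direction can be computed.
- Protocol 8.3.1 names seven ESS situations while SAP 3.2.2 scores eight, which might suggest that one item is imputed for everyone. The form is not in the documents, so this supports only a request to reconcile the lists.

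**What to change.** Amend SAP 3.2.1 and 3.2.2, following the SAP's own PDQ-39 convention:
- **ESS:** prorate the total only if at least 4 of the 8 items are answered; otherwise set it to missing.
- **QUIP-RS:** impute a missing item only from items of the same disorder, and only if at least 2 of its 4 items are answered. Otherwise set that disorder's score, and any total containing it, to missing.
- State that the QUIP-RS rule governs the component, ICD and overall scores. The combined hobbyism-punding component then counts as a total containing two disorders.
- Report the number of totals set to missing, by treatment group.

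The text change is a few sentences. The cost is that some totals become missing, including QUIP-RS totals where only one disorder was skipped and up to 24 other items were answered. PDQ-39 already accepts the same consequence for its summary index. How many totals would be lost cannot be estimated from the documents, which is why the counts by group are needed.
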